8.2.3. Serious Adverse Events

A serious adverse event is any untoward medical occurrence at any dose that:

- Results in death;
- Is life-threatening (immediate risk of death);
- Requires inpatient hospitalization or prolongation of existing hospitalization;
- Results in persistent or significant disability/incapacity (substantial disruption of the ability to conduct normal life functions);
- Results in congenital anomaly/birth defect.

Or that is considered to be:

- An important medical event.

Medical and scientific judgment is exercised in determining whether an event is an important medical event. An important medical event may not be immediately life-threatening and/or result in death or hospitalization. However, if it is determined that the event may jeopardize the subject or may require intervention to prevent one of the other AE outcomes, the important medical event should be reported as serious.

Examples of such events are intensive treatment in an emergency room or at home for allergic bronchospasm; blood dyscrasias or convulsions that do not result in hospitalization; or development of drug dependency or drug abuse.

8.2.4. Hospitalization

Hospitalization is defined as any initial admission (even less than 24 hours) in a hospital or equivalent healthcare facility, or any prolongation of an existing admission. Admission also includes transfer within the hospital to an acute/intensive care unit (eg, from the psychiatric wing to a medical floor, medical floor to a coronary care unit, or neurological floor to a tuberculosis unit). An emergency room visit does not necessarily constitute a hospitalization; however, the event leading to the emergency room visit is assessed for medical importance.

Hospitalization does not include the following:

- Rehabilitation facilities;
- Hospice facilities;
- Respite care (eg, caregiver relief);
- Skilled nursing facilities;
- Nursing homes;
- Same-day surgeries (as outpatient/same-day/ambulatory procedures).

Hospitalization or prolongation of hospitalization in the absence of a precipitating clinical AE is not in itself an SAE. Examples include:

- Admission for treatment of a preexisting condition not associated with the development of a new AE or with a worsening of the preexisting condition (eg, for workup of a persistent pretreatment laboratory abnormality);
- Social admission (eg, subject has no place to sleep);
- Administrative admission (eg, for yearly physical examination);
- Protocol-specified admission during a study (eg, for a procedure required by the study protocol);
- Optional admission not associated with a precipitating clinical AE (eg, for elective cosmetic surgery);
- Hospitalization for observation without a medical AE;

- Preplanned treatments or surgical procedures. These should be noted in the baseline documentation for the entire protocol and/or for the individual subject.

Diagnostic and therapeutic noninvasive and invasive procedures, such as surgery, should not be reported as SAEs. However, the medical condition for which the procedure was performed should be reported if it meets the definition of an SAE. For example, an acute appendicitis that begins during the reporting period should be reported if the SAE requirements are met, and the resulting appendectomy should be recorded as treatment of the AE.

8.3. Severity Assessment

If required on the AE page of the CRF, the investigator will use the adjectives MILD, MODERATE, or SEVERE to describe the maximum intensity of the AE. For purposes of consistency, these intensity grades are defined as follows:	
MILD	Does not interfere with subject's usual function.
MODERATE	Interferes to some extent with subject's usual function.
SEVERE	Interferes significantly with subject's usual function.

Note the distinction between the severity and the seriousness of an AE. A severe event is not necessarily an SAE. For example, a headache may be severe (interferes significantly with the subject's usual function) but would not be classified as serious unless it met one of the criteria for SAEs, listed above.

8.4. Special Situations

8.4.1. Potential Cases of Drug-Induced Liver Injury

Humans exposed to a drug who show no sign of liver injury (as determined by elevations in transaminases) are termed “tolerators,” while those who show transient liver injury, but adapt are termed “adaptors.” In some subjects, transaminase elevations are a harbinger of a more serious potential outcome. These subjects fail to adapt and therefore are “susceptible” to progressive and serious liver injury, commonly referred to as drug-induced liver injury (DILI). Subjects who experience a transaminase elevation above 3 times the upper limit of normal (\times ULN) should be monitored more frequently to determine if they are an “adaptor” or are “susceptible.”

In the majority of DILI cases, elevations in aspartate aminotransferase (AST) and/or alanine aminotransferase (ALT) precede total bilirubin (TBili) elevations ($>2 \times$ ULN) by several days or weeks. The increase in TBili typically occurs while AST/ALT is/are still elevated above $3 \times$ ULN (ie, AST/ALT and TBili values will be elevated within the same lab sample). In rare instances, by the time TBili elevations are detected, AST/ALT values might have decreased. This occurrence is still regarded as a potential DILI. Therefore, abnormal elevations in either AST OR ALT in addition to TBili that meet the criteria outlined below

are considered potential DILI (assessed per Hy's law criteria) cases and should always be considered important medical events, even before all other possible causes of liver injury have been excluded.

The threshold of laboratory abnormalities for a potential DILI case depends on the subject's individual baseline values and underlying conditions. Subjects who present with the following laboratory abnormalities should be evaluated further as potential DILI (Hy's law) cases to definitively determine the etiology of the abnormal laboratory values:

- Subjects with AST/ALT and TBili baseline values within the normal range who subsequently present with AST OR ALT values $>3 \times \text{ULN}$ AND a TBili value $>2 \times \text{ULN}$ with no evidence of hemolysis and an alkaline phosphatase value $<2 \times \text{ULN}$ or not available.
- For subjects with baseline AST **OR** ALT **OR** TBili values above the ULN, the following threshold values are used in the definition mentioned above, as needed, depending on which values are above the ULN at baseline:
 - Preexisting AST or ALT baseline values above the normal range: AST or ALT values >2 times the baseline values AND $>3 \times \text{ULN}$; or $>8 \times \text{ULN}$ (whichever is smaller).
 - Preexisting values of TBili above the normal range: TBili level increased from baseline value by an amount of at least $1 \times \text{ULN}$ **or** if the value reaches $>3 \times \text{ULN}$ (whichever is smaller).

Rises in AST/ALT and TBili separated by more than a few weeks should be assessed individually based on clinical judgment; any case where uncertainty remains as to whether it represents a potential Hy's law case should be reviewed with the sponsor.

The subject should return to the investigator site and be evaluated as soon as possible, preferably within 48 hours from awareness of the abnormal results. This evaluation should include laboratory tests, detailed history, and physical assessment.

In addition to repeating measurements of AST and ALT and TBili, laboratory tests should include albumin, creatine kinase (CK), direct and indirect bilirubin, gamma-glutamyl transferase (GGT), prothrombin time (PT)/international normalized ratio (INR), total bile acids, alkaline phosphatase and acetaminophen drug and/or protein adduct levels. Consideration should also be given to drawing a separate tube of clotted blood and an anticoagulated tube of blood for further testing, as needed, for further contemporaneous analyses at the time of the recognized initial abnormalities to determine etiology. A detailed history, including relevant information, such as review of ethanol, acetaminophen (either by itself or as a coformulated product in prescription or over-the-counter medications), recreational drug, supplement (herbal) use and consumption, family history, sexual history, travel history, history of contact with a jaundiced person, surgery, blood transfusion, history of liver or allergic disease, and potential occupational exposure to chemicals, should be

collected. Further testing for acute hepatitis A, B, C, D, and E infection and liver imaging (eg, biliary tract) may be warranted.

All cases demonstrated on repeat testing as meeting the laboratory criteria of AST/ALT and TBili elevation defined above should be considered potential DILI (Hy's law) cases if no other reason for the LFT abnormalities has yet been found. **Such potential DILI (Hy's law) cases are to be reported as SAEs, irrespective of availability of all the results of the investigations performed to determine etiology of the LFT abnormalities.**

A potential DILI (Hy's law) case becomes a confirmed case only after all results of reasonable investigations have been received and have excluded an alternative etiology.

8.4.2. Exposure to the Investigational Product During Pregnancy or Breastfeeding, and Occupational Exposure

Exposure to the investigational product under study during pregnancy or breastfeeding and occupational exposure are reportable to Pfizer Safety within 24 hours of investigator awareness.

8.4.2.1. Exposure During Pregnancy

For both unapproved/unlicensed products and for marketed products, an exposure during pregnancy (EDP) occurs if:

- A female becomes, or is found to be, pregnant either while receiving or having been exposed (eg, because of treatment or environmental exposure) to the investigational product; or the female becomes or is found to be pregnant after discontinuing and/or being exposed to the investigational product;
- An example of environmental exposure would be a case involving direct contact with a Pfizer product in a pregnant woman (eg, a nurse reports that she is pregnant and has been exposed to chemotherapeutic products).
- A male has been exposed (eg, because of treatment or environmental exposure) to the investigational product prior to or around the time of conception and/or is exposed during his partner's pregnancy.

If a subject or subject's partner becomes or is found to be pregnant during the subject's treatment with the investigational product, the investigator must report this information to Pfizer Safety on the CT SAE Report Form and an EDP supplemental form, regardless of whether an SAE has occurred. In addition, the investigator must submit information regarding environmental exposure to a Pfizer product in a pregnant woman (eg, a subject reports that she is pregnant and has been exposed to a cytotoxic product by inhalation or spillage) to Pfizer Safety using the EDP supplemental form. This must be done irrespective of whether an AE has occurred and within 24 hours of awareness of the exposure. The information submitted should include the anticipated date of delivery (see below for information related to termination of pregnancy).

Follow-up is conducted to obtain general information on the pregnancy and its outcome for all EDP reports with an unknown outcome. The investigator will follow the pregnancy until completion (or until pregnancy termination) and notify Pfizer Safety of the outcome as a follow-up to the initial EDP supplemental form. In the case of a live birth, the structural integrity of the neonate can be assessed at the time of birth. In the event of a termination, the reason(s) for termination should be specified and, if clinically possible, the structural integrity of the terminated fetus should be assessed by gross visual inspection (unless pre-procedure test findings are conclusive for a congenital anomaly and the findings are reported).

If the outcome of the pregnancy meets the criteria for an SAE (ie, ectopic pregnancy, spontaneous abortion, intrauterine fetal demise, neonatal death, or congenital anomaly [in a live-born baby, a terminated fetus, an intrauterine fetal demise, or a neonatal death]), the investigator should follow the procedures for reporting SAEs.

Additional information about pregnancy outcomes that are reported to Pfizer Safety as SAEs follows:

- Spontaneous abortion includes miscarriage and missed abortion;
- Neonatal deaths that occur within 1 month of birth should be reported, without regard to causality, as SAEs. In addition, infant deaths after 1 month should be reported as SAEs when the investigator assesses the infant death as related or possibly related to exposure to the investigational product.

Additional information regarding the EDP may be requested by the sponsor. Further follow-up of birth outcomes will be handled on a case-by-case basis (eg, follow-up on preterm infants to identify developmental delays). In the case of paternal exposure, the investigator will provide the subject with the Pregnant Partner Release of Information Form to deliver to his partner. The investigator must document in the source documents that the subject was given the Pregnant Partner Release of Information Form to provide to his partner.

8.4.2.2. Exposure During Breastfeeding

Scenarios of exposure during breastfeeding must be reported, irrespective of the presence of an associated SAE, to Pfizer Safety within 24 hours of the investigator's awareness, using the CT SAE Report Form. An exposure during breastfeeding report is not created when a Pfizer drug specifically approved for use in breastfeeding women (eg, vitamins) is administered in accord with authorized use. However, if the infant experiences an SAE associated with such a drug's administration, the SAE is reported together with the exposure during breastfeeding.

8.4.2.3. Occupational Exposure

An occupational exposure occurs when, during the performance of job duties, a person (whether a healthcare professional or otherwise) gets in unplanned direct contact with the product, which may or may not lead to the occurrence of an AE.

An occupational exposure is reported to Pfizer Safety within 24 hours of the investigator's awareness, using the CT SAE Report Form, regardless of whether there is an associated SAE. Since the information does not pertain to a subject enrolled in the study, the information is not recorded on a CRF; however, a copy of the completed CT SAE Report Form is maintained in the investigator site file.

8.4.3. Medication Errors

Other exposures to the investigational product under study may occur in clinical trial settings, such as medication errors.

Safety Event	Recorded on the CRF	Reported on the CT SAE Report Form to Pfizer Safety Within 24 Hours of Awareness
Medication errors	All (regardless of whether associated with an AE)	Only if associated with an SAE

8.4.3.1. Medication Errors

Medication errors may result from the administration or consumption of the investigational product by the wrong subject, or at the wrong time, or at the wrong dosage strength.

Medication errors include:

- Medication errors involving subject exposure to the investigational product;
- Potential medication errors or uses outside of what is foreseen in the protocol that do or do not involve the participating subject.

Such medication errors occurring to a study participant are to be captured on the medication error page of the CRF, which is a specific version of the AE page.

In the event of a medication dosing error, the sponsor should be notified immediately.

Whether or not the medication error is accompanied by an AE, as determined by the investigator, the medication error is recorded on the medication error page of the CRF and, if applicable, any associated AE(s), serious and non-serious, are recorded on an AE page of the CRF.

Medication errors should be reported to Pfizer Safety within 24 hours on a CT SAE Report Form **only when associated with an SAE**.

9. DATA ANALYSIS/STATISTICAL METHODS

Detailed methodology for summary and statistical analyses of the data collected in this study is outlined here and further detailed in a SAP, which will be maintained by the sponsor. The SAP may modify what is outlined in the protocol where appropriate; however, any major modifications of the primary endpoint definitions or their analyses will also be reflected in a protocol amendment.

9.1. Sample Size Determination

Approximately 15 subjects per arm are planned in this study for a total of approximately 45 subjects. Assuming an approximate 5% premature withdrawal rate, this will ensure a minimum of 42 subjects complete the study. With this sample size the power to detect a 25% mean reduction in MRI-PDFP relative to placebo is at least 79% using a 1-sided Type I error rate of 0.1. This calculation assumes the pooled SD of the log-relative change of 0.36 (based on an internal study).

9.2. Efficacy Analysis

The primary analysis population for all efficacy analyses will include all randomized subjects who received at least 1 dose of study medication (Full Analysis set).

9.2.1. Analysis of the Primary Endpoint

The primary endpoint will be the relative change from baseline at Day 15 in whole liver PDFP. Baseline will be the closest measurement prior to first dose on Day 1. An analysis of covariance (ANCOVA) will be performed on log-transformed relative change with treatment and baseline diabetic status as factors, log-transformed baseline whole liver PDFP value as a covariate. Estimates of the mean relative changes between each active dose and placebo at Day 15, and the corresponding 80% confidence interval (CI) will be obtained from the model. Each comparison of PF-06865571 dose with the placebo will be performed at a Type I error rate of 10% (1-sided). No adjustment for multiple comparisons will be made. If the model does not fit the data group medians and their differences from the placebo median will be presented. The details will be provided in the SAP.

Descriptive summaries of the observed values and percent change from baseline in whole liver PDFP for each treatment group will also be produced.

CCI

9.3. Pharmacokinetic Analysis

The PK concentration population will be defined as all randomized subjects who received at least 1 dose of PF-06865571 and in whom at least 1 plasma PK concentration value is reported. The PK parameter analysis population will be defined as all randomized subjects who received at least 1 dose of PF-06865571 and who have at least 1 of the PK parameters of interest calculated. PK samples from placebo samples will not be routinely analyzed.

9.3.1. Derivation of Pharmacokinetic Parameters

The PK parameters for PF-06865571 will be derived from the concentration-time profiles as data permit. The various PK parameters to be assessed in this study, their definition and method of determination are outlined in Table 7. Actual PK sampling times will be used in the derivation of PK parameters.

Table 7. Definition of Steady State (Day 14) Plasma PK Parameters for PF-06865571

Parameter	Definition	Method of Determination
AUC _{tau}	Area under the plasma concentration-time profile from time zero to time tau (τ), the dosing interval	Linear/Log trapezoidal method
C _{max}	Maximum plasma concentration during the dosing interval	Observed directly from data
T _{max}	Time for C _{max}	Observed directly from data as time of first occurrence
CL/F	Apparent clearance	Dose/AUC _{tau}
C _{min}	Minimum plasma concentration during the dosing interval	Observed directly from data
PTR	Peak-to-trough ratio	C _{max} /C _{min}

The above listed PK parameters will be summarized descriptively by dose. Relationships between PF-06865571 PK and safety and/or efficacy endpoints may also be explored, but may not be included in the final CSR.

CCI

CCI

CCI

9.6. Safety Analysis

AEs, ECGs, BP, pulse rate, and safety laboratory data will be reviewed and summarized on an ongoing basis during the study to evaluate the safety of subjects. Any clinical laboratory, ECG, BP, and pulse rate abnormalities of potential clinical concern will be described. Safety data will be presented in tabular and/or graphical format and summarized descriptively, where appropriate.

Medical history and physical examination information collected during the course of the study will be considered source data and will not be required to be reported, unless otherwise noted. However, any untoward findings identified on physical examinations conducted during the active collection period will be captured as AEs, if those findings meet the definition of an AE. Data collected at screening that are used for inclusion/exclusion criteria, such as laboratory data, ECGs, and vital signs, will be considered source data, and will not be required to be reported, unless otherwise noted. Demographic data collected at screening will be reported.

9.6.1. Electrocardiogram Analysis

Changes from baseline for the ECG parameters QT interval, heart rate, QTcF interval, PR interval, and QRS interval will be summarized by treatment and time.

The number (%) of subjects with maximum postdose QTcF values and maximum increases from baseline in the following categories will be tabulated by treatment:

Safety QTcF Assessment

	Borderline (msec)	Prolonged (msec)
Absolute value	≥450 - <480	≥480
Absolute change	30-<60	≥60

In addition, the number of subjects with corrected and uncorrected QT values ≥500 msec will be listed.

In addition, an attempt will be made to explore and characterize the relationship between plasma concentration and QT interval length using a PK/PD modeling approach. If a PK/PD relationship is found, the impact of subject factors (covariates) on the relationship will be examined. The analysis, if conducted, may not be reported.

9.7. Interim Analysis

Interim analyses may be performed to assess efficacy and/or safety after at least 50% of the planned subjects, ie, approximately 21 subjects, complete the study. Interim analysis results may be used for internal business decisions regarding future study planning, stopping for futility, conducting a sample size reestimation, or adapting the study after the interim analysis. Before any interim analysis is instigated, the details of the objectives, decision criteria, dissemination plan, and method of maintaining the study blind as per Pfizer's SOPs will be documented and approved in an internal review committee (IRC) charter. In addition, the analysis details will be documented and approved in an interim analysis SAP or final SAP.

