1. VERSION HISTORY

This Statistical Analysis Plan (SAP) for study C2541005 is based on the protocol dated 27FEB2018.

Table 1. Summary of Major Changes in SAP Amendments

SAP Version	Change	Rationale
1	Not Applicable	Not Applicable

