2. INTRODUCTION

This SAP provides the detailed methodology for summary and statistical analyses of the data collected in study C2541005. This document may modify the plans outlined in the protocol; however, any major modifications of the primary endpoint definition or its analysis will also be reflected in a protocol amendment.

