5.1. Hypotheses and Decision Rules

The following null hypotheses will be tested for each endpoint:

1. 300 mg PF-06865571 Q12H is equal in effect to placebo.
2. 50 mg PF-06865571 Q12H is equal in effect to placebo.

The alternative hypotheses corresponding to the above null hypotheses will be the following 2-sided hypotheses:

1. The effect of 300 mg PF-06865571 Q12H is different from the effect of placebo.
2. The effect of 50 mg PF-06865571 Q12H is different from the effect of placebo.

The Type I error rate (α -level) used with the decision rule for the primary objective is 10% (1-sided). No adjustment for multiple comparisons will be made.

Interim analyses may be performed to assess efficacy and/or safety after at least 50% of the planned subjects, ie, approximately 21 subjects, complete the study. Interim analysis results may be used for internal business decisions regarding future study planning or stopping for futility. As such no adjustment in the Type I error rate is proposed.

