7. INTERIM ANALYSES

Interim analyses may be performed to assess efficacy and/or safety after at least 50% of the planned subjects, ie, approximately 21 subjects, complete the study. Interim analysis results may be used for internal business decisions regarding future study planning or stopping for futility. Before any interim analysis is instigated, the details of the objectives, decision criteria, dissemination plan, and method of maintaining the study blind as per Pfizer's SOPs will be documented and approved in an internal review committee (IRC) charter. In addition, the analysis details will be documented and approved in an interim analysis SAP.

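### Does the SAP's shorter list of interim uses leave the Type I error of the primary test unprotected?

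*Protocol*

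**What the plan says.** Protocol 9.7 makes the interim optional, for efficacy and/or safety, once at least half of the planned subjects (about 21) have completed. The results may serve internal decisions on future study planning, "stopping for futility, conducting a sample size reestimation, or adapting the study after the interim analysis". That makes four uses.

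SAP 5.1 and SAP 7 carry almost the same sentence, but the decisions are those "regarding future study planning or stopping for futility". That makes two uses. SAP 5.1 then draws its conclusion: "As such no adjustment in the Type I error rate is proposed".

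The documents also differ on where the details go. Protocol 9.7 says "the analysis details will be documented and approved in an interim analysis SAP or final SAP"; SAP 7 says "the analysis details will be documented and approved in an interim analysis SAP". Both require an approved internal review committee charter, covering objectives, decision criteria and protection of the blind, before any interim starts.

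On how the documents relate, Protocol 9 says "The SAP may modify what is outlined in the protocol where appropriate" and SAP 2 says "This document may modify the plans outlined in the protocol". Both reserve a protocol amendment for major changes to the primary endpoint definition or its analysis. SAP 1 states that the SAP "is based on the protocol dated 27FEB2018".

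**The concern.** Read side by side, the two lists do not match, and the SAP never says that it has withdrawn sample size re-estimation or adaptation. Its case for leaving the error rate alone begins with the words As such, so it rests on the two-item list. Someone working from the protocol alone could take all four uses as open and assume that the same conclusion covers them.

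It would not. If the second-stage size, or the choice of dose, depends on the observed interim effect and the ordinary final test is then used, the 10% 1-sided error need not hold. The setting adds to the worry. The sponsor is unblinded (Protocol 3.1 and 5.2), there is no data monitoring committee, and any review committee would consist of sponsor employees or designees (Protocol 9.8). The stake would be an inflated false-positive rate for the primary liver-fat comparison.

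**Working it through.** **Inputs from the documents.** 1-sided alpha 0.10 for each dose against placebo, with no multiplicity adjustment (Protocol 9.2.1, SAP 5.1). 25% reduction relative to placebo, SD of the log-relative change 0.36, 45 randomized, at least 42 completers (Protocol 9.1). Ratio 1:1:1 (Protocol 3.1), so 14 completers per arm. Interim at about 21 completers, and 21/42 = 50%.

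**Assumptions not in the documents.** 7 completers per arm at the interim, the futility boundaries, and every re-estimation or dose-selection rule below.

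**1. The plan's own power figure.** Effect |ln 0.75| = 0.2877. Standard error 0.36 × √(2/14) = 0.1361. Ratio 0.2877/0.1361 = 2.114. Power = Φ(2.114 − 1.2816) = 79.7%. With the noncentral t it is 78.8% on 26 df and 79.1% on 39 or 37 df. The stated figure of at least 79% is reproduced, and it fits only the 1-sided reading: 2-sided 0.10 gives 68.1%.

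**2. The uses that the SAP names.** Planning a later study does not touch this trial's test. For futility, let R be rejection at the end and S a futility stop. A false positive then needs R without S, and P(R and not S) ≤ P(R) = 10% for any boundary. With information fraction 0.5, final Z = (z1 + z2)/√2, and rejection if Z > 1.2816:

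| Futility rule | 1-sided error |
|---|---|
| none | 10.0% |
| stop if z1 ≤ 0 | 9.5% |
| stop if conditional power under the observed trend is below 10% | 9.0% |

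The cost falls on power: a stop at z1 ≤ 0 lowers it from just under 80% to about 78%. The SAP's conclusion is right for its list.

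**3. The two uses found only in the protocol.** Here the answer depends on a rule that nobody has written. Given z1, with m subjects per arm in the second stage and the ordinary pooled test, the rejection probability is P(Z2 > [1.2816·√(7+m) − √7·z1]/√m), integrated over z1. Second-stage caps are 14 / 28 / 63 per arm.

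- m set to reach 80% conditional power under the observed trend, otherwise kept at 7, with a stop at z1 ≤ 0: 9.4 / 9.3 / 9.2%.
- The same, but m goes to the cap when the target is missed: 9.9 / 10.0 / 10.1%.
- The same with no futility stop: 11.0 / 12.0 / 12.9%.
- Least favourable m between 7 and the cap, with a stop at z1 ≤ 0: 10.0 / 10.3 / 10.4%.
- Least favourable m when the second stage may also shrink below 7, with the same stop: 13.0 / 13.3 / 13.4%. Without the stop: 14.2 / 15.2 / 16.2%.
- No limit on m at all: the bound 0.10 + exp(−1.2816²/2)/4 = 21.0%.

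Dropping the dose with the smaller interim effect (simulation, 7 per arm in each stage): the kept dose is falsely positive in 14.8% of null trials, which is 7.4% per planned comparison. The planned pair of unadjusted tests gives at least one false positive in 16.7%.

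So the error lies anywhere from below 10% to about 21%. That range describes invented rules, not this plan.

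**4. Do the texts contradict each other?** Protocol 9.7 says what the results may be used for; it obliges nobody to re-estimate or adapt. A SAP that takes up two of four permitted uses stays inside the protocol. SAP 5.1 and SAP 7 give the same two-item list, and the error-rate statement is tied to it, which points to deliberate narrowing. The same holds for the place of documentation: the protocol offers two, and the SAP picks one of them.

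**The case for a change.** The strongest case for an edit is that a general power to modify the protocol does not show that this omission is a modification. The authors of the charter and of the interim analysis SAP work from both documents. The charter requirement makes them record decision criteria, but does not tell them which uses are allowed. Neither document says that an efficacy-driven change would need an error-controlling method. With an open sponsor and a single sentence as the price, settling the point beforehand seems sensible.

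Part of this stands. The lists do differ, the SAP does not mention a withdrawal, and its error-rate statement would not cover re-estimation or dose selection if either were revived. It could not then be carried over unchanged.

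But the edit would only write down what the SAP already implies. An analyst following the SAP does planning or futility and nothing else. Anyone wishing to re-estimate or adapt on efficacy must first obtain approval of objectives, decision criteria and analysis details, and that is where a rule and its error control would be set. If that changed the primary analysis in a major way, both documents call for a protocol amendment. Adaptation after a safety look also falls under the protocol's wider wording, so trimming Protocol 9.7 to the SAP's two items would remove something useful.

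**Conclusion.** The difference in wording is real but does not call for a change. The SAP makes a permitted narrowing of a permissive protocol list, and its decision not to adjust is correct for the uses it names: the 1-sided error per dose is at most 10% under any futility boundary, and 9.5% or 9.0% under the two illustrated. No rule in either document produces inflation. The excess that re-estimation or dose selection might cause depends entirely on assumed rules, so it cannot be counted against this plan. The interim is optional, approval of criteria and methods comes first, and the final ANCOVA, sample size and reported intervals stay as they are. The conclusion rests on reading the SAP's list as the operative one; if an efficacy-driven re-estimation or adaptation were later proposed, its error control would have to be settled in the charter and the interim analysis SAP, as the documents already require for any interim.
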